3.2.1 Primary Outcome Measures

23
24 There are three major areas of safety and tolerability that will be assessed in this phase I
25 trial. The outcome measurements will be compared between the two treatment groups
(Intervention v placebo) with intent to treat analysis.

26
27
28 **1. Evidence of invasive infection resulting from the administration of *L. reuteri* DSM
29 17938.** Baseline and daily temperature measurements will be made during the study
30 period. Complete hemogram with differential count obtained at baseline, on day 5, and
31 on day 28. Vital signs will be monitored daily during the administration of the treatment
32 (days 1-5). The evaluation of all febrile episodes will be done and include a physician
33 exam and the evaluation of blood smears for malaria and blood cultures for the
34 evaluation of possible bacteremia.

35
36 Specific outcome parameters in this category include:

37
38 a. Mean daily temperature
39 b. Incidence of fever on study days 1-5
40 c. Frequency of temperature readings categorized as fever (adjusted for number of
41 subjects per group)
42 d. Number of episodes of *L. reuteri* bacteremia

43
44 **2. Clinical tolerance.** The inclusion of a placebo group will allow for comparisons of daily
45 symptom measurements to be compared between the treatment and placebo group.
The symptoms will be monitored for at household visits, and will be graded as
adverse events according to defined criteria. Symptoms monitored as AEs include
fever, nausea/upset stomach, vomiting, diarrhea, irritability, rash, pruritis, and
wheezing or bronchospasm. Diagnostic microbiology will be performed on all stool
specimens from subjects who develop diarrhea during the 90 days following initiation
of therapy.

46
47 Specific outcome parameters in this category include:

- 1 a. Frequency and severity of symptoms monitored as AEs (adjusted for number of
2 subjects per group)
- 3 b. Frequency of all AEs (adjusted for number of subjects per group)
- 4 c. Frequency of SAEs (adjusted for number of subjects per group)

5

6

7 **3. Evidence of toxicity resulting from the *L. reuteri* DSM 17938 preparation.**

8 Participants will have baseline, day 5, and day 28 assessment of hematologic status and
9 renal and hepatic function. Assessment of renal function will include blood urea nitrogen
10 (BUN) and creatinine (Cr). Assessment of hepatic toxicity will include transaminases

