5 STUDY ENROLLMENT AND WITHDRAWAL

1

2 **5.1 Subject Inclusion Criteria**

3

4

5 In order to be eligible to participate in this study, a subject must meet all of the following
6 criteria:

7

- 8 • Have a parental permission form signed by both parents
- 9 • Be between 8 weeks to 24 months of age with no preexisting exclusion criteria
- 10 • Have parents who are willing to comply with all planned study procedures and be available for planned study visits for 3 months.

1
2 **5.2 Subject Exclusion Criteria**

3
4 1) No enrollment of family members in households where any of the following are
5 present:
6
7 a. Another study participant in the household
8
9 b. Presence of immune suppressed individuals or use of immunosuppressive
10 agents (including but not limited to corticosteroids, methotrexate, etc.) by any
11 household member
12
13 c. Presence of a serious congenital anomaly or chronic medical condition that in
14 the opinion of the investigators would contraindicate participation in any household
15 member, including history of gastrointestinal surgery, chronic gastrointestinal
16 illness, abnormal intestinal anatomy, or abnormal bowel functionality
17

18 The following risk factors are at the level of the individual child:

19
20 2) Allergy to penicillin, cephalosporins, clindamycin or gentamicin
21 3) History of antibiotic use in the last 30 days
22 4) Use of probiotic products within the past 30 days, including masato (local
23 product with fermenting bacteria) and yogurt products containing live
24 bacterial cultures.
25 5) History of diarrheal illness within the past 30 days (See definition in Protocol
26 Appendix B)
27 6) Presence of fever or a pre-existing adverse event monitored in the study
28 (See Protocol Appendix B Definitions of AEs for specific adverse events
29 monitored in the study)
30 7) Positive results on serum diagnostic tests for antibodies to HIV.
31
32 8) Presence of severe anemia, defined as serum hemoglobin \leq 7 gm/dL
33
34 9) Out of range laboratory values for total leucocyte count, BUN, Creatinine,
35 AST, ALT, and total bilirubin monitored as potential adverse events, as
36 described in Appendix E.
37 10) Pre-enrollment stool sample (collected within 14 days of day 1 of the study)
38 is positive for *L. reuteri* by PCR.
39
40

1 **5.3 Strategies for Recruitment and Retention**

2 The community where recruitment will occur has been a research site for the current

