3 group for the last fifteen years. During this time we have had successful recruitment
4 and retention for intensive birth cohort studies and have recruited and trained nurses
5 and health care workers and a study team from the area. The community is
6 experienced in research participation which aids recruitment and retention of study
7 subjects.^{9,36-42}

10 **5.4 Treatment Assignment Procedures**

11 Treatment assignment is based on the order in which subjects complete screening and
12 are assigned a study code. This study code is the same as the treatment vial ID
13 number.

14 **5.4.1 Randomization Procedures**

15 **Randomization.** Upon satisfactory completion of screening, participants will be assigned
16 a study code (different from the PID that accompanied screening data) that is associated
17 with a list completed by the project biostatistician and shared with the individual at
18 BioGaia preparing the treatment vials. This sequential code is associated with treatment
19 vials randomized to one of two treatment groups (T or P) on a 2:1 (T:P) basis with the first
20 randomized subject receiving the first study vial, etc. All vials are identical (see labelling
21 section below) and the Treatment ID on the vial matches the study code number.

22 **5.4.2 Masking Procedures**

23 This is a double masked trial. Only the project biostatistician has the table linking
24 treatment assignment to randomization code. Unmasking of the rest of the study team
25 will occur only when the database is locked for final analysis or if a clinical situation
26 arises in which the PI feels unmasking is necessary for the treatment of a SAE.

27 **5.4.3 Reasons for Withdrawal**

28 A study subject will be discontinued from participation in the study prior to completing 5
29 days of study product administration if:

30 A subject may be discontinued from the study for the following medical or
31 administrative reasons:

- 1 1) Occurrence of an AE, which in the judgment of the investigator suggests an
2 unacceptable risk to the subject to receive a test product (The investigator will
3 follow the subject until satisfactory resolution of the AE or the AE is determined
4 to be stable.) A likely example in this community might be the development of
5 severe falciparum malaria during the product administration period.
- 6 2) Development of ANY condition fulfilling one of the exclusion criteria (except for
7 out of range laboratory values);
- 8 3) Subject/parental request.

9

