34 participants meet these exclusion criteria. If the stool specimen is positive for *L. reuteri*,
35 the child will be excluded from the study (exclusion criterion #10). Subjects with negative
36 stool PCR results for *L. reuteri*, negative HIV serology and adequate hemoglobin levels
37 (per inclusion/exclusion criteria) will progress to the initial medical examination. The
38 screening will take place in a nationally certified (INS- certified) clinical trial center in the
39 community of Santa Clara. Subjects with positive results on HIV serology or inadequate
40 hemoglobin levels will receive appropriate counseling and referral to medical services
41 available in the community for patients with these conditions. HIV seropositive children
42 will be referred to the only HIV referral (Hospital Regional de Loreto) directly by the study
43 MD.
44
45 5) Subjects not excluded on the basis of laboratory tests will receive a baseline
46 medical exam. A baseline assessment for presence of symptoms monitored for as AEs

1 will be done on Day 1 prior to randomization and receipt of initial dosing of study product.
2 Subjects who have developed an exclusionary clinical adverse event since onset of the
3 screening process (e.g. diarrhea, bronchospasm) will not be allowed to be randomized,
4 but may be re-evaluated for inclusion at a later date by restarting the screening process
5 for a period of thirty days following the onset of the AE.

6

7 7.4 Product Administration period

8

9 On days 1-5 participants will attend the study clinic to receive study product. The health
10 worker will administer LR or PL and this treatment will be continued once daily for a total
11 of five days. Participants will be monitored for 20 minutes. Any dose vomited within 20
12 minutes of administration will be repeated. Vital signs are monitored and symptoms are
13 recorded.

14 Study participants will have daily visit at the community-based study clinic on study days
15 1-5 to detect symptoms, adverse events, and to administer the test article (LR or PL)
16 under directly observed therapy. Parents of subjects will be instructed to in the use of a
17 diary card, provided by the study personnel, to record any symptoms the infant
18 experienced during the treatment phase and the first 28 day follow-up period. Parents of
19 subjects will be instructed to record both solicited AEs (clinical symptoms listed as

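### Section 5.4.3 item 2 allows, and on one lead-in requires, a child to leave the study for fever, diarrhea or antibiotic use during dosing, with no commitment to the remaining scheduled safety follow-up

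*Combined protocol and SAP*

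**What the plan says.** Section 5.4.3 (Reasons for Withdrawal) has two lead-ins before its numbered list. The first is "A study subject will be discontinued from participation in the study prior to completing 5" days of product, and it ends without a list of its own. The second is "A subject may be discontinued from the study for the following medical or" administrative reasons. Both speak of leaving the study, not of stopping product. Item 2 of the list is "Development of ANY condition fulfilling one of the exclusion criteria (except for" laboratory values out of range).

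The exclusion criteria in section 5.2 include:

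- criterion 3: "History of antibiotic use in the last 30 days"
- criterion 5: "History of diarrheal illness within the past 30 days"
- criterion 6: "Presence of fever or a pre-existing adverse event monitored in the study"

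Section 3.2.1 names "Incidence of fever on study days 1-5" as primary outcome 1b, lists diarrhea among the primary tolerance symptoms, and plans an intent-to-treat comparison. Section 11.2 analyses children as assigned once they have had one dose and does not impute missing data. Section 5.4.4 plans no replacement.

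For an SAE, sections 6.3 and 7.4 stop product and keep the child in planned follow-up. Section 6.3 does the same after a blood culture positive for *L. reuteri*. Item 2 carries no such sentence. Item 1 promises follow-up only until the event resolves or is stable.

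**The concern.** A child who develops a primary outcome during dosing can be taken out of the study because of it. Later safety data would then be missing for a reason tied to the outcome, and nothing in the analysis plan makes up for that. A child with a mild fever would also have less assured follow-up than a child with an SAE.

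The gap reaches the invasive-infection question. Under sections 7.4 and 9.2.2 a child with grade 3 or 4 fever, or who looks toxic, has a blood culture, and treatment may start at the physician's discretion. The fever already meets criterion 6, and an antibiotic would meet criterion 3, before the culture result is known. If the child is not admitted and meets no other SAE criterion, the follow-up commitment in 6.3 does not apply. Such a child is among those a safety trial most needs to keep observing.

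The data at risk are later adverse events, repeat fever readings (outcome 1c) and the bloods behind the toxicity outcomes.

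**Working it through.** The plan gives no figure to reproduce, so the check has two parts.

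**1. What follow-up does the text assure for a child discontinued under item 2?**

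| Section | Commitment | Covers the full schedule for this child? |
|---|---|---|
| 5.4.3 item 2 | none | no |
| 5.4.4 | every attempt at complete data; at the least, parents are asked to allow visits for vital signs and illness history | no: framed around withdrawal of consent, and the minimum omits bloods |
| 7.7 | termination visit for any non-completer; visits continue if the participant agrees | no: depends on agreement, and does not require staff to continue after an investigator's decision |
| 9.2.1, 9.4 | adverse events within 90 days documented and followed to resolution or stability | no: tied to events, schedules no bloods or temperatures |
| 6.3, 7.4 | planned follow-up continues | yes, but only after an SAE (6.3 also after an *L. reuteri*-positive culture) |

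Fever, diarrhea and antibiotic use are clear triggers. Other monitored symptoms are arguable. Criterion 6 refers to pre-existing events, whereas section 7.3 treats a newly developed event as exclusionary before randomization: "Subjects who have developed an exclusionary clinical adverse event since onset of the" screening process cannot be randomized.

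**2. What could one child lose?**

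Inputs, from Appendix A, after baseline:

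- bloods: days 5 and 28 (2)
- temperatures: days 1-5, 8, 12, 15, 18, 24 and 28 (5 + 6 = 11)
- adverse-event contacts: the same 11 days plus day 90 (12)
- diary: days 1-28 (28)

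The loss after an exit at the day-k visit is the number of items with a nominal day later than k, assuming nothing is collected afterwards.

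| Exit visit | Bloods lost | Temperatures lost | Adverse-event contacts lost | Diary days lost |
|---|---|---|---|---|
| Day 2 | 2 of 2 | 11 - 2 = 9 of 11 | 12 - 2 = 10 of 12 | 28 - 2 = 26 of 28 |
| Day 3 | 2 of 2 | 11 - 3 = 8 of 11 | 12 - 3 = 9 of 12 | 28 - 3 = 25 of 28 |
| Day 4 | 2 of 2 | 11 - 4 = 7 of 11 | 12 - 4 = 8 of 12 | 28 - 4 = 24 of 28 |

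Appendix A allows a 48-hour window for bloods without saying in which direction. If it may be used early, the day-5 blood can be taken from day 5 - 2 = 3. A day-3 or day-4 exit then loses 1 of 2 bloods, and a day-2 exit still loses both. If the section 5.4.4 minimum is achieved, temperature and illness-history losses fall to none, but the blood losses remain.

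Two items are left out on purpose. Stools are not counted, because section 11.2 restricts carriage data to children who complete 5 days of therapy. A child who has had the fifth dose is not counted, because the first lead-in applies only before 5 days of product are completed.

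With 60 children at 2:1 there are 40 active and 20 placebo, so one child is 1/40 = 2.5% of the active arm or 1/20 = 5% of placebo.

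**The case against.** The strongest reply is that the protocol never meant to remove these children. Several places support it. The numbered list sits directly under the permissive lead-in. Sections 7.4 and 9.2.2 describe how a febrile child is examined and cultured during dosing, without mentioning exit. Section 3.2.1 calls for microbiology on diarrheal stools over the 90 days from the start of therapy, which includes the dosing days. Section 11.1 separates events that stop study drug from events that lead to withdrawal from the study. Section 7.7 already lets visits continue if parents agree, and parents of a child discontinued by the investigator have not withdrawn.

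Most of this stands as evidence of intent, and it makes total loss of follow-up less likely. It does not change what 5.4.3 says, and none of these places secures the two post-baseline bloods for such a child.

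A reader might infer more than the text supports:

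- *That exit is mandatory.* The two lead-ins conflict, so this is unresolved.
- *That the triggering fever or diarrhea drops out of the analysis.* The event is recorded, and the child stays in the safety analysis under the one-dose rule.
- *That the rule favours the active product.* No symptom rates are given by arm, and the effect on mean temperature or mean laboratory values could go either way.
- *That the shedding analysis suffers.* A child stopped before five doses is outside it in any case.

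**Conclusion.** The point holds as a defect in a stated rule; it does not show that data will be lost. Item 2 permits, and on one reading requires, removal from the study for events that are themselves primary outcomes, and firm continuation of planned follow-up is written only for SAEs and *L. reuteri*-positive cultures.

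The per-child worst case in the tables rests on Appendix A's nominal days and on nothing being collected after an exit on days 2-4. Sections 5.4.4, 7.7, 9.2.1 and 9.4 make that extreme less likely, and the bloods are the least protected item. The trial-level size cannot be derived, because the documents give no rates for the triggers and use of item 2 may be discretionary. If one arm has more early fever or diarrhea, more of its later data would be at risk, but the direction of any resulting bias cannot be stated. In a trial of 60 children whose primary objective is safety, this should be corrected.

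**What to change.** In section 5.4.3, use one verb and make items 1 and 2 reasons to stop study product only. Whether stopping product is mandatory or left to the investigator is for the sponsor to decide. Extend the sentence in section 6.3 that continues planned follow-up to every child who has received at least one dose, through day 90 and including the day-5 and day-28 bloods, unless parents withdraw consent. Keep item 3 and section 5.4.4 for withdrawal of consent.

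The cost is a wording change in two sections. No children, visits or samples are added to the schedule; those already planned are carried out for these children.

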6 STUDY INTERVENTION/INVESTIGATIONAL PRODUCT

6.1 Study Product Description

6.1.1 Acquisition

The product will be obtained from BioGaia (Stockholm, Sweden). It is likely that a single shipment will be sufficient to cover the needs of the phase 1 infant trial as both product and placebo have a shelf life of 18 months. If unanticipated circumstances delay the start of phase 1 infant trial, a repeat shipment will be requested no later than 4 months prior to the expiration date of the product due to expire. It is possible that subsidiaries or agencies contracted by BioGaia packaging and preparation of product or placebo.

6.1.2 Formulation, Packaging, and Labeling

Formulation of test product and placebo are the following:

1. Active Product: Description *Lactobacillus reuteri* 17938 suspended in sunflower oil, medium chain triglyceride oil, silicone dioxide. Total viable count of *L. reuteri* 17938 1 x 10^8 CFU/5 drops. Study products supplied generally contain 2-8 x 10^8 CFU/5 drops from the manufacturer, in order to guarantee a potency of at least 1 x 10^8 CFU/5 drops by the product expiration date.

2. Placebo: Composition Sunflower oil, medium chain triglyceride oil and silicon dioxide. Total viable count of *L. reuteri* is zero CFU/ 5 drops.

The product is packaged in a single multidose amber glass vial per participant at a volume several times that required for the 5 day dose. The individual vials are packed in reinforced boxes for shipping with a temperature logging.

The label contains the following information

Name of Study: Safety of *Lactobacillus reuteri* in healthy children ages 2-24 months in Peru

BioGaia Drops Dose: 5 drops per dose Store at 2-8C Shake well before using

Test article code: xxxxxxxx Discard 10 days after opening Exp date: yyyy Batch No:

zzzz

Responsible MD: [name], Johns Hopkins University

Manufactured for BioGaia AB, Stockholm Sweden

Caution: New Drug- Limited to investigational use

6.1.3 Product Storage and Stability

1 The study product is to be stored at 2-8°C in multidose subject specific amber vials.
2
3
4 Once opened, the contents of the vial should be dispensed in 10 days.
5
6 The product is administered in the clinical trial center by a member of the study staff in
7 a designated product administration space. This space is adjacent to the dedicated
8 product storage space in the clinic. The dosing is done once daily for 5 days and
9 programmed based on participant and staff convenience. Details of product
10 prescription and vial treatment confirmation upon each dose administration are
11 described in the Manual of Procedures.

12
13 **6.2 Dosage, Preparation and Administration of Study**
14 **Intervention/Investigational Product**
15

16 The individual treatment vial is prepared and labelled by BioGaia. No reconstitution or
17 dilution is needed. The vial will be inverted gently 5 times to assure homogenization and
18 five drops of the suspension will be administered orally to the study subject by study staff
19 that is blinded as to the treatment status of the individual.

6.3 Modification of Study Intervention/Investigational Product for a Subject

If the child vomits or spits up within 20 minutes of administration, the dose will be re-administered. If a subject has a SAE during the 5 day treatment window or if the child has blood cultures that are positive for *L. reuteri* product administration will be discontinued in that individual. All safety and planned protocol follow-up will continue.

6.4 Accountability Procedures for the Study Intervention/Investigational Product(s)

The study PI is accountable for the investigational product and the appropriate conduct of the clinical trial in compliance with ICH GCP guidelines and Peruvian laws and regulations.

Details on product accountability, including initial certificate of analysis, product accountability including the documentation of international cold chain transport and evaluation of product viability will be held onsite for evaluation by external monitors. The trial product will be shipped from the provider BioGaia and or suppliers by World Courier to Peru with temperature monitoring. Procedures for the temperature controlled movement and tracking of study product between the laboratory and the clinic is outlined in the MOP. Tests for product viability and the detection of possible contaminants are detailed in laboratory SOPs and detailed in the product assurance plan. At the end of the study all unused product will be autoclaved prior to disposal.

6.5 Assessment of Subject Compliance with Study Intervention/Investigational Product

All treatments are directly administered by study staff. Missed dosages will be documented. In the case that a subject is not available on a study day a 1 day window will be tolerated for the administration of a single missing dose. The daily dose is restricted to a single dose per day, so in this case, the dosing interval would occur over a 6 day period. Follow-up schedule would not be altered from the programmed plan. No more than a single dose will be given this window- if a second dose were to be missed, it would be documented in a protocol deviation form and analyzed per group treatment assignment. Subsequent doses are done at 24 hour intervals from the last dose, but visit scheduling cannot be altered after the first dose is administered.

6.6 Concomitant Medications/Treatments

All concomitant medications, including herbal or natural therapies are documented at

1 baseline or that are taken by the subject during the follow-up period will be documented
2 on CRFs. Information on concomitant medications is solicited at baseline, upon each
3 dosage with study product (D1-D5), D8, D12, D15, D18, D24, and D28.
4
5 Treatment for sepsis will be standard weight based doses of ceftriaxone and gentamicin.
6 If the project clinician suspects that the product is a likely source of the sepsis (no source
7 of lower respiratory tract infection, urinary tract infection, or diarrheal illness noted)
8 clindamycin will be added to the treatment. Treatment guidelines are reviewed with study
9 physicians and treatment is available on site to facilitate the rapid treatment of sepsis.

